Power was computed for an effect size (d) of 0.37, a small-medium effect size to be conservative, based on similar intervention studies in similar facilities comparing groups in terms of high levels of medication adherence and changes in HIV risk behavior.^[4] The computations assume an intraclass correlation (ICC) of 0.500, as we assume conservatively large dependence within participant overtime. Over a 44-month period, 300 participants taking PrEP and enrolled in methadone-maintenance treatment at the APT Foundation (see letter of support) will be recruited and randomly assigned to the two study cells (150 per cell). The criterion for significance (alpha) has been set at 0.05. The test is 2-tailed, which means that an effect in either direction will be interpreted. Given these assumptions (for the effect size, ICC), criteria (for alpha and tails), and plans (for the number of clusters and sample size within cluster), the study will have power of 98.5% to yield a statistically significant result. These same assumptions (for the ICC), and plans (for the number of subjects and time points within subject), the study will allow us to report the effect size (d) with a standard error of approximately 0.089. In order to maintain that power level, we must 288 retain patients at post-intervention, 276 at 3-month follow-up, 258 patients at 6-month follow-up, and 224 patients at 9-month follow-up. Even in the event that only 71% of participants complete the final 9-month follow-up assessment, which would be a conservative estimate based on the previous randomized controlled trials in the same facility among the same patient population, the proposed ample size will still provide sufficient power (94.5%) to detect the expected range of effect sizes.

For EACH Participant Population State Describe the Study Population(s): [Describe the participant population(s) including gender, ethnicity, income, level of education and age range.]

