Participants for trial will be included who are: 1) Are 18 years of age or older; 2) Meet DSM-V criteria for opioid-dependence and are enrolled in methadone maintenance drug treatment at the APT Foundation, Inc.; 3) Were confirmed to be HIV-negative and started on PrEP in the past week; 4) Report unsafe injection drug use practices or unprotected sex within the past 3 months; 5) Have a cell phone; 6) Are able to read and understand the questionnaires, ACASI, and informed consent form; 7) Available for the full duration of the study with no anticipated circumstances impeding participation (e.g., pending charges, jail term). Individuals unable to provide consent and who are actively suicidal, homicidal, or psychotic as assessed by trained research staff under the supervision of the PI who is a licensed clinical psychologist in Connecticut will be excluded.

We plan to recruit 60% men and 40% women (18 years or older) in order to adequately represent the proportion of men and women in the New Haven community. Recruiting 60% men and 40% women should pose no problem given that the men constitute 61% of the APT Foundation MMP (Methadone Maintenance Program), the patient population from which the subjects for the proposed studies will be recruited. However, given that women typically represent 39% of APT MMP population, we plan to increase our efforts to recruit women into the methadone treatment program by posting advertisements at the APT Foundation substance abuse treatment program.

Minorities. We plan to recruit 50% English-speaking minorities; 40% African American and 10% English-speaking Latino/Latina. These target figures are representative of African-Americans and Latino/ Latinas in the community.

Enrollment of UConn Students and/or Employees: [Will UConn students be enrolled? If so, describe if these students include those who any key research personnel teaches, or for whom any key research personnel has responsibility. Will UConn employees be enrolled? If so, describe if these employees

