IMB construct measures. Data collected at all assessment points will include our measure of IMB model constructs,^[3] including (a) Information - HIV risk- and PrEP-related knowledge; (b) Motivation - readiness to change and intentions to change PrEP adherence and change HIV risk behavior; (c) Behavioral Skills - PrEP adherence skills and HIV risk reduction skills; and (d) Behavioral Outcomes - HIV risk and HIV risk reduction behaviors and PrEP adherence. Behavioral skills will also be assessed as in prior controlled trials^[4, 18, 29-31] by having patients demonstrate (a) the specific steps necessary to properly clean a needle/syringe and (b) demonstrate the specific steps to properly select and apply a male and female condom using replicas. Ratings of videotaped demonstrations of these procedures by staff blind to treatment assignment has shown excellent inter-rater reliability (inter-rater reliability = 0.98).^[30] The demonstrated behavioral skills score is derived by calculating the percentage of steps performed correctly on each skill.

Urine toxicology. Four-panel (heroin, cocaine, oxycodone, and benzodiazepine) immunoassay (I/A) urinalyses (with confirmation of positive results) will be conducted at T₀, weekly during the 8-week intervention phase, at T₈, and at follow-ups (T₂₀, T₃₂, T₄₄) to detect the most common illicit substances of abuse in this patient population. As in our prior NIDA-funded studies, urine samples will be shipped to Clinical Science Laboratory Inc. ([name]) and will be analyzed using the Abbott Tdx method, which has been shown to be a reliable, precise, and cost-effective system.

Weekly Assessments. During the 8-week intervention period, weekly urine toxicology will be performed to detect illicit substance use including opiates, cocaine, and benzodiazepine. In addition, a weekly self-report of illicit drug use, other high-risk behaviors, and PrEP adherence will be obtained. All of the self-report measures given at weekly assessments will be administered using ACASI. A similar instrument has been used by our team in an RCT at the research performance site.^[19, 32] Using a time-line follow-back

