Hypotheses related to the specific aims: This study is designed to test the primary hypothesis for PWUD prescribed PrEP that the experimental intervention (E=CHRP-BB) is significantly more effective vs. the control condition (S: time-and-attention matched intervention), for the primary outcome of high levels of PrEP adherence (e.g., ≥ 700 fmol/punch or ≥ 4 pills/week)^[25, 26] and secondary outcome of HIV risk reduction behavior. The null hypothesis is that CHRP-BB is not superior to control condition, expressed as $H_0: p_E = p_S$, where p_E is the proportion of participants in CHRP-BB who demonstrate high levels of adherence (e.g., ≥ 700 fmol/punch or ≥ 4 pills/week)^[25, 26] and are free from HIV risk behavior T₃₂post-intervention. Our alternative hypothesis is that the experimental intervention is superior to the control condition, and is expressed as $H_1: p_E > p_S$. Prior to analyzing treatment effects, the degree of pre-test equivalence between experimental and control groups on key variables (e.g., baseline demographics and clinical characteristics) will be evaluated. Baseline data will be evaluated via t-tests and ANOVAs on continuous items when normal or Kruskal-Wallis when we have a non-normal distribution of those items and chi-square tests of categorical items to evaluate pretest equivalence between and within the experimental and control groups. The presence of moderate/severe NCI will be included as a covariate to control for each of the dependent variables. We will use the Bonferroni approach^[43] to correct for alpha inflation with a 0.05 family-wise alpha. Variables in which inequality at baseline is identified will be used as covariates in further analyses to address potential non-equivalence across conditions.^[44] Differential attrition analyses will also be conducted on the data set to assess differential attrition by condition between baseline and subsequent measurements. A series of ANOVAs parametric or non-parametric of Condition (intervention, control) by Retention (retained, not retained) will be conducted on continuous pretest measures^[45]. Any variable influencing differential attrition will be included as a covariate in subsequent analyses.

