Main outcomes analysis plan: The framework for testing the study hypotheses will be to compare differences between the two conditions (CHRP-BB vs. Control) on the main outcome variables. Separate logistic regression models will be used to assess the log odds of having high levels of PrEP adherence and being free from injection or sexual transmission risk behaviors at T₄₄ post-intervention using intervention assignment as a binary coded predictor while controlling for any potential confounders. As an alternative analytical plan for assessing the impact of the two intervention arms on adherence to PrEP, we will use

questionnaires, and collection of urine sample is minimal and adds no risk beyond those normally associated with methadone maintenance treatment. Assessment measures and content of the intervention will involve sensitive and explicit topics related to sexual behavior and substance use. This is necessary given the nature of the intervention and practices that confer risk for HIV infection. However, participants may feel awkward or embarrassed when hearing about or being asked to provide information related to sexual activity. The consent procedure informs participants that sexual behaviors will be explicitly covered in measures and intervention content. Counseling staff will have been trained to observe for signs of subject emotional distress in relation to topic presentation and to employ techniques that prevent, reduce or minimize embarrassment, discomfort, or atypical distress.

Some participants may experience increased anxiety as a result of participating in the intervention. Realistic sensitization and accurate vulnerability self-appraisal are desirable and necessary to motivate behavior change efforts. The investigator is experienced in presenting risk reduction information in ways that link risk to avoidable and modifiable behaviors and risk reduction to the adoption of behavior changes. Counseling staff will observe participants for evidence of becoming overly anxious and will utilize techniques to assure that threat sensitization and vulnerability perceptions are realistic. Research staff will also be knowledgeable of social services that some participants may need, and will assist participants in accessing local resources in areas such as alcohol and other drug abuse treatment, entitlement, and supports for those in or leaving abusive relationships.

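### Baseline amount of risk behavior is not a pre-specified covariate in the T44 risk-behavior model, so adjustment for it depends on data-driven rules and precision may be lost

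*Combined protocol and SAP*

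**What the plan says.** - **Entry.** The inclusion criteria require that participants "Report unsafe injection drug use practices or unprotected sex within the past 3 months".
- **Outcome.** The hypotheses section names a "secondary outcome of HIV risk reduction behavior". The main outcomes analysis plan gives it a separate logistic model for "being free from injection or sexual transmission risk behaviors at" T44, "using intervention assignment as a binary coded predictor while controlling for any potential confounders". The confounders are not named.
- **Covariates.** The hypotheses section fixes one: "The presence of moderate/severe NCI will be included as a covariate to control for each of the dependent variables". For the rest, "Variables in which inequality at baseline is identified will be used as covariates in further analyses", and a variable found to influence differential attrition is also added.
- **Baseline data.** The section on IMB construct measures schedules collection at every assessment point, including "Behavioral Outcomes - HIV risk and HIV risk reduction behaviors and PrEP adherence". A T0 measure of risk behavior is therefore planned.
- **Randomization.** The urn procedure names sex and race as examples of balancing variables and is stratified by NCI. The amount of risk behavior is not named there.

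**The concern.** The usual baseline adjustment for a binary outcome is the same variable at T0. Here the entry rule makes that variable nearly constant, so it can explain almost nothing. What remains informative is the baseline amount: someone who reports one unsafe act in three months is more likely to report none at T44 than someone who reports sixty.

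The visible plan collects risk behavior at T0 but does not commit its level to the model. It may enter through a baseline difference test, an attrition analysis or a judgment about confounding. The first two depend on the data, and the third is open. A baseline test asks whether the arms differ by chance, not whether the variable predicts the outcome, so a strong predictor that happens to be balanced is left out. At stake is precision for this outcome, together with a model whose covariate set is settled only after the data are seen.

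**Working it through.** **1. The plan's own power figure.** Inputs from the sample size section: d = 0.37, 150 per arm, two-sided alpha 0.05, and "The computations assume an intraclass correlation (ICC) of 0.500". The design section gives five assessments.

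- SE = sqrt{[(1 + 4 × 0.5)/5] × 2/150} = sqrt(0.6 × 0.01333) = 0.0894; the plan states 0.089.
- Power = Φ(0.37/0.0894 − 1.96) = 98.5%, as stated.
- The same formula gives 94.7% at 112 per arm (the 224 target) and 93.7% at 71% retention (213 people, 106.5 per arm; the plan states 94.5%).

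These figures describe an average of five measures. The T44 risk model uses one binary result from one visit, and the visible text gives no power for it.

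**2. Gain from the covariate, latent normal model.** Assumptions: a normally distributed risk level with correlation ρ between T0 and T44; entry if the T0 level is at or above a cut-off; response if the T44 level is below it; an intervention shift of 0.37; 112 per arm. The share q of the source population with any risk is not in the documents, so 50%, 70% and 90% are shown. Simulated power of the logistic model:

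| ρ | q | arm only | plus baseline level | gain (points) |
|---|---|---|---|---|
| 0.50 | 50% | 66.1% | 68.8% | 2.7 |
| 0.50 | 70% | 59.1% | 62.9% | 3.8 |
| 0.50 | 90% | 39.1% | 42.2% | 3.1 |
| 0.70 | 50% | 74.4% | 80.2% | 5.8 |
| 0.70 | 70% | 66.4% | 71.8% | 5.4 |
| 0.70 | 90% | 40.5% | 46.6% | 6.1 |

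**3. Gain from the covariate, gamma-Poisson model.** Assumptions: act counts with mean μ per 3 months and dispersion k (neither is in the documents); at least one act at entry; zero acts over an equal window at T44 to respond; acts halved in the intervention arm; 112 per arm; log baseline count as covariate.

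| μ | k | arm only | plus log count | gain (points) |
|---|---|---|---|---|
| 2 | 0.5 | 73.5% | 81.3% | 7.8 |
| 5 | 0.5 | 56.8% | 67.7% | 10.9 |
| 5 | 1 | 65.9% | 73.9% | 8.0 |
| 10 | 0.5 | 42.3% | 54.7% | 12.4 |

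**4. Validity with no effect.** In the same four count settings, the two arms respond at the same rate (for example 20.6% and 20.7%). Type I error is 3.3% to 4.9% without the covariate and 4.2% to 5.5% with it.

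**5. Does selection at entry cost power?** In the latent normal model, the arm-only test with the entry rule is compared with the same cut-off and no entry rule (normal approximation, ρ = 0.50, 112 per arm). No-effect response with the rule is P(Y < c | X ≥ c).

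| q | no-effect response with rule | power with rule | power without rule |
|---|---|---|---|
| 50% | 33.3% | 66% | 59% |
| 70% | 20.5% | 60% | 58% |
| 90% | 7.5% | about 41% | 41% |

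Selection leaves power about equal or higher.

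**The case against.** **Baseline risk is not excluded.** It can enter as a confounder or through either data-driven rule. That is correct, and it limits the point to a lack of pre-specification. The outcome is also labelled secondary, although freedom from risk behavior also appears in the stated null hypothesis.

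**The text is incomplete.** The main outcomes analysis plan breaks off mid-sentence, and the reference on count regression is cited nowhere in the visible text. A count analysis, or a fuller covariate list, may sit in what is not shown. This stands, so the absence of a count model is not criticised here.

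A reader might infer more than the documents support:

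- *That the outcome exactly reverses the entry rule.* The T44 look-back window and list of acts are not visible, and the two wordings differ.
- *That people who become risk-free by chance lower the power.* Some will cross the line with no true change, but step 5 shows no resulting loss of power. They arise in both arms and do not bias the comparison.
- *That the plan would read a within-arm fall as benefit.* Its stated framework compares the two conditions, and the trajectory question is set within a randomized design with a matched control.
- *That a yes/no endpoint is wrong.* Being free from risk is a legitimate target. Preferring counts is partly a matter of taste.

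**Conclusion.** The point holds as a matter of precision and pre-specification. The visible covariate rules guarantee adjustment for NCI only, and the entry criterion leaves the amount of baseline risk as the useful form of the baseline measure. The treatment comparison is valid either way.

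The size is modest and depends on the model: about 3 to 6 power points at 224 completers on the latent normal scale (ρ 0.50 to 0.70), and about 8 to 12 with halved, overdispersed counts. Source-population prevalence, mean acts, dispersion and the form of the effect are all assumptions; the 0.50 correlation and d = 0.37 are the plan's. Both models favor adjustment in every setting tabulated. The conclusion also assumes that the missing text does not already fix this covariate.

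**What to change.** In the T44 risk-behavior logistic model, name the T0 risk level as a fixed covariate alongside NCI, regardless of any baseline test or attrition result. If acts are counted, one form is log(1 + number of unsafe injection and unprotected sex acts at T0); otherwise use the T0 risk score. State the form before the data are unblinded.

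The cost is one sentence in the analysis plan and one degree of freedom. It needs no new visits or patients, and T0 risk behavior is already to be assessed. The odds ratio becomes conditional on baseline risk and should be labelled so. A baseline-adjusted count analysis is at most an optional supportive analysis and may already be planned. If the full text already fixes this covariate, pointing to it settles the matter.

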treatment care and being on PrEP will remain constant and the experimental CHRP-BB intervention will be compared to a time-and-attention-matched control condition. We will assess participants at baseline (T_0), immediately post-intervention (8 weeks; T_8) and follow-ups at 3- (T_{20}), 6- (T_{32}), and 9-month (T_{44}) post-intervention measurement points. This approach will allow us to examine whether CHRP-BB outcomes are superior to the Control condition in the short-term as well as examining the trajectory of PrEP adherence and HIV risk reduction over time. Importantly, this approach will allow a clear examination of the decay and/or emergence of intervention effects.^[5] The proposed research is also designed to allow us to precisely examine the relative cost and cost-effectiveness of each intervention with regard to both individual (efficacy: e.g., PrEP adherence, HIV risk reduction behavior) and population-level health outcomes (effectiveness: e.g., new HIV infections prevented, life years gained, quality of life). Importantly, we will also examine the barriers and facilitators to optimal implementation of the CHRP-BB intervention.

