All opioid-dependent patients enrolled in methadone maintenance treatment will be referred for initial screening. As another precaution, we plan to screen up to 40% more patients than will be needed to meet the proposed sample size. Therefore 420 patients will be screened (i.e., 9 patients per month). In the screening session, conducted by a member of the research staff, determination will be made as to whether the participant meets study inclusion criteria. If so, the participant will be provided with a description of the study. After meeting eligibility criteria, providing informed consent, verifying comprehension of the terms of the study – including being started on PrEP in the past week, and completing the baseline assessment, participants will be randomized to receive, in addition to standard of drug treatment care: (a) 4 weekly group sessions and the 8-week booster session that comprise the CHRP-BB intervention or (b) 4 weekly group sessions and the 8-week booster session that comprise the time-and-attention matched control condition. Participants will be randomized using a computerized “urn” randomization to ensure adequate representation of women and minorities. This technique modifies randomization probabilities based on prior composition of study conditions and reduces the possibility that imbalances between the study groups on variables such as sex and race will occur by chance. Randomization will be stratified by the presence of moderate/severe NCI levels based on the brief inventory of neuro-cognitive impairment (BINI),^[6] to ensure that the proportion of participants at highest risk for poor outcome is equal between intervention arms. The clinicians supervising the MMP will be blind to which intervention the subject is receiving. The standard of care and the intervention conditions will be:

Standard of Drug Treatment Care. Participants in both conditions will receive routine services as part of their enrollment in APT’s methadone maintenance program, which includes daily methadone and case management consisting of a minimum of one hour of monthly contact with a counselor/case manager.

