Experimental Condition. Patients assigned to the bio-behavioral community-friendly health recovery program (CHRP-BB) will: (a) receive the standard of drug treatment care, as described above, (b) have started PrEP the prior week, and (c) participate in four weekly 50-minute HIV risk reduction and PrEP adherence groups and one booster session, all led by two facilitators trained and supervised by [name], the PI and licensed clinical psychologist. Our theory-based (IMB model of health behavior change),^[3, 7] manual-guided, HIV risk reduction and PrEP adherence intervention is an integrated evidence-based intervention that uses a coping skills training approach to primary prevention and is delivered in a small group modality by two trained intervention facilitators using a motivational enhancement therapeutic style to address high risk drug- and sex-related HIV risk behaviors and PrEP adherence. Importantly, the CHRP-BB intervention includes specific behavioral and mHealth strategies designed and tested to accommodate difficulties stemming from moderate to severe NCI^[8] (see manual in Appendix). Participants will receive daily text message to remind them to take PrEP. Participants will receive text message at the time as they requested in the “Text Messaging Reminder Timing Determination” form (see attached). Participants will also receive text message for appointment reminders. This directly addresses the otherwise detrimental impact of cognitive impairment on

HIV-positive individuals. These measures have been consistently used in our prior clinical trials,^[19-21] confirming high test-retest reliability (.88 to .98).^[22]

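### Both arms are treated in group sessions, but the main T44 logistic models and the power statement make no allowance for session-group correlation: probably a small effect, and cheap to fix

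*Combined protocol and SAP*

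**What the plan says.** The paragraph on screening and randomisation assigns individuals to one of two conditions, each added to standard drug-treatment care. One is "4 weekly group sessions and the 8-week booster session that comprise the CHRP-BB intervention"; the other is "4 weekly group sessions and the 8-week booster session that comprise the time-and-attention matched control condition". The Experimental Condition section adds that CHRP-BB "is delivered in a small group modality by two trained intervention facilitators".

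The main outcomes analysis plan compares the arms at T44 by separate logistic regressions for high PrEP adherence and for freedom from transmission risk behaviour, "using intervention assignment as a binary coded predictor while controlling for any potential confounders". The section on hypotheses adds covariates only: neurocognitive impairment, variables unbalanced at baseline, and variables linked to differential attrition.

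The sample-size paragraph uses one intraclass correlation, 0.500, explained "as we assume conservatively large dependence within participant overtime". It reports 98.5% power for d = 0.37 with 300 participants and a standard error of about 0.089, and it requires "224 patients at 9-month follow-up".

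The only visible provision for dependence between people is in the section on fidelity and cross-contamination. Known partners go to the same condition, and couple status becomes a factor in the outcome analyses if partners exceed 5% of participants.

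**The concern.** People who attend the same four sessions and booster share facilitators, discussion and each other's influence, so their outcomes may be correlated. An ordinary logistic regression treats all participants as independent. With a positive group ICC, its standard error for the treatment effect is too small, its interval too narrow and its p-value too optimistic. Group delivery in both arms means the problem is not confined to one side of the comparison.

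The 0.500 correlation in the power statement does not cover this. It describes one person's repeated measurements, and it is fully used in reaching 98.5%.

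The plan already regards dependence between partners as worth handling. Session groups involve far more participants, yet the main models have no matching step.

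**Working it through.** **1. The plan's own power figure.** Inputs from the sample-size paragraph: N = 300 (150 per arm), d = 0.37, two-sided alpha 0.05, within-person ICC 0.5. The design description gives five visits (T0, T8, T20, T32, T44).

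- Variance factor for a five-visit mean: (1 + 4 × 0.5)/5 = 0.60.
- SE = √(4/300 × 0.60) = 0.0894, against 0.089 stated.
- Power = Φ(0.37/0.0894 − 1.960) = 98.5%, as stated.

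Both figures are reached with participants as the only clusters, so no session-group allowance is contained in them.

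**2. Group sizes (assumed).** The documents give no group size. Accrual of 300 over 44 months is 150/44 = 3.41 per arm per month. Groups formed monthly would enrol M = 3.41; groups formed every two months, 6.82. Multiplying by planned retention, 224/300, gives m = 2.55 or 5.09 analysed at T44.

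**3. Single-visit T44 test.** Design effect DE = 1 + (m − 1) × ICC. True type I error = 2 × [1 − Φ(z/√DE)], with z = 1.960. Power uses SE = √(4/224 × DE) and d = 0.37. With DE = 1, SE = 0.1336 and power = Φ(0.37/0.1336 − 1.960) = 79.1%.

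Example, m = 2.55 and ICC 0.05: DE = 1 + 1.55 × 0.05 = 1.08; 1.960/√1.077 = 1.89; true error 5.9%.

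**4. Five-visit basis.** Baseline precedes randomisation, so a group effect can act on only four of the five visits: factor (4/5)² = 0.64. Variance = 4/300 × [0.60 + 0.64 × (M − 1) × ICC], assuming the group effect does not fade by T44.

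| Groups formed | Assumed ICC | DE at T44 | True error at nominal 5% | T44 power, N = 224 | Five-visit power, N = 300 |
|---|---|---|---|---|---|
| either | 0 | 1.00 | 5.0% | 79.1% | 98.5% |
| monthly | 0.02 | 1.03 | 5.4% | 77.8% | 98.1% |
| monthly | 0.05 | 1.08 | 5.9% | 76.0% | 97.3% |
| monthly | 0.10 | 1.15 | 6.8% | 73.1% | 95.8% |
| two-monthly | 0.02 | 1.08 | 6.0% | 75.9% | 97.4% |
| two-monthly | 0.05 | 1.20 | 7.4% | 71.3% | 95.1% |
| two-monthly | 0.10 | 1.41 | 9.9% | 64.5% | 90.1% |

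The gap between 98.5% and 79.1% comes from testing one visit rather than averaging five, and from the smaller N. It is a separate matter.

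**5. If Bonferroni applies.** The hypotheses section states a 0.05 family-wise alpha, but its scope and the number of tests are unclear. If each of two main models is tested at 0.025 (z = 2.241), the true per-test errors at ICC 0.02/0.05/0.10 are 2.7/3.1/3.7% (monthly) or 3.1/4.1/5.9% (two-monthly). T44 power falls from 70.1% to 68.6/66.5/63.1% or 66.3/61.1/53.6%.

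**6. Simulation check.** Beta-binomial outcomes, proportion 0.5, 112 of 150 per arm retained at random, no covariates, 20,000 runs per setting. Ranges cover repeat runs and equal or unequal group sizes. The unclustered logistic test at nominal 5% rejected:

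- ICC 0: 5.1–5.5%;
- ICC 0.02: 5.3–5.9% with 44 groups per arm, 6.2–6.7% with 22;
- ICC 0.05: about 6–7% with 44 groups, 7.5–8.5% with 22;
- ICC 0.10: 7.4–8.2% with 44 groups, 10.3–11.2% with 22.

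A cluster-robust t test stayed at 4.5–5.2% in every setting, including ICC 0.

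**The case against.** - **Lost text may deal with it.** The control-arm description is missing and the analysis section breaks off within an alternative analysis; later references to count models and mediation are cited nowhere in the available text. This stands as a limit. The sentence defining the main models is complete, and the point is confined to those models and the power statement. A later general statement on variance estimation would answer it.
- **The larger groups fit poorly.** Eligibility requires that participants "Were confirmed to be HIV-negative and started on PrEP in the past week", and T8 falls at eight weeks. Waiting up to two months to fill a closed group would strain both. This stands: small monthly groups or rolling entry are at least as plausible, and the two-monthly rows deserve less weight.
- **The favoured case shows little.** The unclustered test already rejects slightly above 5% with no group correlation, so at ICC 0.02 with small groups the simulated excess is hard to separate from the test's own. This stands for that setting; at ICC 0.05 and above the excess is visible. In the other direction, random retention makes the closed form slightly low: the relevant multiplier is (M − 1) × 224/300 = 1.80 rather than 1.55, which moves 5.9% to 6.05% at ICC 0.05.
- **A low ICC is likely.** T44 is nine months after the intervention, and participants are to have no contact outside routine services. Accepted; this is why the effect is called probably small.
- **The visit is unsettled.** The hypotheses section places the null hypothesis at T32, the main models at T44. The figures here follow T44 and would change somewhat at T32, where 258 are planned. That conflict needs its own reconciliation.

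**Conclusion.** The point holds. Both arms are delivered in groups, the main T44 models contain no allowance for it, and the stated 98.5% and 0.089 leave none in the power statement. Whether this does harm depends on a group ICC that the documents do not give: at zero the planned standard errors are valid, and at any positive value they are too small.

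The most plausible size, with 2.5 analysed per group and an ICC of 0.02 to 0.05, is a true error of about 5.4% to 5.9% at nominal 5%. The corresponding T44 power is 76% to 78% rather than 79%, and five-visit power is 97% to 98% rather than 98.5%. These figures assume fixed, non-overlapping groups; under rolling entry they are approximate. This is a worthwhile and inexpensive improvement, not a serious flaw. Confidence in the size is moderate.

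**What to change.** 1. Record a session-group identifier for every participant from the session records. If entry is rolling, record an entry-cohort identifier instead and say that it is approximate, because cohorts overlap.
2. Fit the main T44 logistic models with a cluster-robust variance on that identifier: for example, GEE with an independence working correlation, a small-sample correction, and a t reference on the number of clusters minus 2. The planned marginal odds ratio and its point estimate are unchanged; only the standard error and reference distribution change.
3. Give known partners a single cluster identifier, merging their groups' identifiers if they attended different groups.
4. State in the sample-size paragraph that 98.5% assumes no session-group correlation, and give the range if there is some.

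**Cost.** SAP wording and one variable; facilitators already complete forms for each session. The interval will usually be slightly wider. If the true group ICC is zero, single-visit power at alpha 0.05 falls from 79.1% to 78.2% with 44 groups per arm (88 − 2 = 86 df, critical value 1.99), or to 77.2% with 22 (44 − 2 = 42 df, 2.02). At alpha 0.025 it falls from 70.1% to 68.7% or 67.2%.
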